Following the baseline interview and stratification, the research assistant will randomize Veterans to Treatment as Usual or Treatment as Usual plus Relational Agent Intervention. As described above, Veterans will be stratified by the severity of alcohol use disorder. Within strata, block randomization with variable block sizes will be used to ensure that treatment groups balance over time. The block sizes will be randomly varied and of sufficient size to minimize the ability of any study staff or Veterans to guess the next random allocation assignment. Randomization assignments will be generated using computer-generated random numbers and will be available immediately to the research assistant upon entering the Veteran-participant's information and responses from the baseline interview. We will use the randomization procedure available in RedCAP. After the research assistant determines the random allocation assignment of the Veteran-participant, the Veteran will be directed either to proceed to his scheduled clinical encounter (Treatment as Usual) or will be introduced to the Relational Agent Intervention.

Relational Agent Intervention-procedure

When a Veteran is allocated to Relational Agent + Treatment as Usual, the research assistant will first enroll the participant into the Relational Agent system (entering the participant's ID, gender, given name, and presence/absence of AUD), introduce the Veteran to the Relational Agent, explain briefly how the Relational Agent works, then allow the Veteran to complete the Relational Agent program in privacy using headphones.

We are using AUDIT scores and previous substance abuse treatment in addition to the MINI as conservative indicators of the need for specialty treatment. Negative results on these measures will result in a brief intervention only. A positive result for alcohol abuse or dependence from the MINI during the baseline assessment, previous substance abuse treatment, or a score higher than 20 on the AUDIT will trigger a referral to specialty treatment at the end of the intervention.

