Data collection and storage. Research interviews and other relevant data will be collected via the REDCap program behind the VA firewall and stored on a VA server. REDCap allows the assignment of different levels of access privileges and audit trails, thus ensuring proper data management and minimizing mistakes. For instance the Project Manager can be the only one who is allowed to edit data, while RAs can be allowed to enter and download data only. At the time of this IRB amendment (2/9/16), we were given permission to use REDCap while it is under review for VA Research by VACO. If REDCap is disallowed, we will identify and propose alternative systems.

The Relational Agent software is installed on VA tablet/laptops and the database for the program will be on a VA server. The software installed on the tablets includes custom software created by Northeastern University computer scientists, Unity software used for animation, and XXAMP, a web application. Also, the system uses MySQL database on both the tablets and the VA server. It is installed on the tablets for local storage, and as insurance against being unable to run the program if wifi connection is unavailable. It gets backed up to the VA servers. Both the database on tablets and VA server and the transmission to the server can be encrypted.

Study Design for Aim 2

This study is a mixed design, with Alcohol Severity Groups and Treatment Arms as between-groups variables and Time of Testing (Baseline vs. 3-Month Follow-up) as a repeated measure variable. The main focus of this initial RCT is to compare Treatment as Usual (TAU) to TAU plus the Relational Agent Intervention

(TAU+RA) on (a) alcohol consumption, (b) rates of brief intervention, and (c) rates of referral to treatment. We will use a stratified randomization scheme, stratifying on whether a Veteran is a risky drinker or has the more severe designation of an alcohol use disorder, to ensure that the two study groups balance on severity. Veterans allocated to Treatment as Usual will continue to receive all usual care as delivered in the PCC. Veterans allocated to Treatment as Usual plus Relational Agent Intervention will interact with the Relational Agent as soon as possible following the baseline assessment, and still receive usual care.

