GEE utilizes inverse probabilities to correct for any bias associated with NMCAR, with participants who are Completers weighted with the drop-out probabilities of participants with the “same” characteristics at Baseline. These weighting values will be estimated from the logistic analyses described above.

The overall design is a three-way mixed-design with Treatment Arm (Treatment as Usual vs. Treatment as Usual plus Relational Agent Intervention) and Drinking Severity (Risky vs. Alcohol Use Disorder) and 2 occasions (0 and 3 months) as the repeated measures design. We will take an intent-to-treat approach to the analysis; Veterans will be included in our primary analyses regardless of their level of adherence with their assigned intervention. Participants who do not complete the 3-month follow-up assessment will be considered to have missing data for that assessment and will not be included in the analysis of intervention effectiveness. The secondary outcomes, which will be “incidence rates”, will be tested by logistic regression.

Primary Hypothesis: The Relational Agent will be more effective than Treatment as Usual in reducing the quantity and frequency of alcohol use.

Our primary analyses of the effectiveness of Treatment as Usual vs. Treatment as Usual plus Relational Agent Intervention will focus on measurement outcome variables at the **3-month follow-up**. Separate analyses will be performed for the two primary outcome measures: number of drinking days per week (frequency) and average drinks per drinking day (quantity), both reported over a month. Here we describe the analytic approach for the outcome of quantity of alcohol use (average drinks per drinking day); the approach for frequency will be analogous. Initially our analysis will be through analysis of covariance models. We will include baseline values of the outcome variable as a covariate in these models, so our analyses may be interpreted as focusing on the change in outcome from baseline to three month follow-up. If any key characteristics of our sample were found to differ between groups, we will enter those as covariates as well.

Secondary Hypothesis: The Relational Agent will be more effective than Treatment as Usual in improving rates of brief intervention.

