For our secondary outcome of increased rate of delivering brief intervention, we will compare the two study groups on the proportion of patients receiving brief intervention through the chi-square test. Logistic regression will be used to calculate odds ratios and 95% confidence intervals in order to describe differences in rates of brief intervention between groups. To further examine baseline patient characteristics that predict brief intervention, and control for any covariates found to differ between treatment groups at baseline, we will develop a multivariable logistic regression model predicting rate of brief intervention from baseline characteristics as well as indicator variables representing the intervention group and presence/absence of alcohol use disorders.

Secondary Hypothesis: The Relational Agent will be more effective than Treatment as Usual in improving rates of referral to specialty treatment.

Secondary analysis also includes a comparison of referral rates, and analyses similar to those described for the secondary Hypothesis above will be employed. We will compare study groups on the proportion of patients referred through the chi-square test. Since we expect that Veterans with alcohol use disorders will be more likely to be referred regardless of group, we will test this hypothesis separately, i.e., we will use chi-square to compare rates of referral based solely on presence or absence of alcohol use disorders. Logistic regression will be used to calculate odds ratios and 95% confidence intervals in order to describe differences in referral rates between groups. To further examine baseline patient characteristics that predict brief intervention, and control for any covariates found to differ between treatment groups at baseline, we will develop a multivariable logistic regression model predicting referral rates from baseline characteristics as well as indicator variables representing the intervention group and presence/absence of alcohol use disorders.

Additional exploratory hypotheses:

Negative consequences for alcohol use, as measured by the SIP, may also decrease as a result of intervention, and this hypothesis will be explored as well through a random effects linear regression model.

Sample Size and Power Considerations

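### The plan names competing tests for the two secondary outcomes without saying which decides, and the chi-square named for the arm comparison ignores the randomisation stratum, which costs power for referral if severity strongly predicts it

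*Combined protocol and SAP*

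**What the plan says.** Three statements bear on how the arms are compared on receipt of brief intervention and on referral.

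- The two Secondary Hypothesis paragraphs give the arm comparison to a chi-square: "we will compare the two study groups on the proportion of patients receiving brief intervention through the chi-square test", and for referral, "We will compare study groups on the proportion of patients referred through the chi-square test". Logistic regression follows there to supply odds ratios and 95% confidence intervals.
- Earlier in Statistical Analysis, in the paragraph on the overall design, the plan says: "The secondary outcomes, which will be “incidence rates”, will be tested by logistic regression". No covariates are listed.
- Each Secondary Hypothesis paragraph ends with a multivariable logistic model containing "indicator variables representing the intervention group and presence/absence of alcohol use disorders". Its purpose is given as "To further examine baseline patient characteristics that predict brief intervention, and control for any covariates found to differ between treatment groups at baseline". That clause, still naming brief intervention, also stands in the referral paragraph.

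On allocation, Study Design for Aim 2 describes a scheme "stratifying on whether a Veteran is a risky drinker or has the more severe designation of an alcohol use disorder", and Randomization adds: "Within strata, block randomization with variable block sizes will be used to ensure that treatment groups balance over time".

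For referral, the plan expects Veterans with alcohol use disorder (AUD) to be referred more often in either arm. The Stratification section has the agent recommend referral to everyone in the AUD stratum, but in the risky stratum only after certain responses. The plan makes no comparable statement about severity and brief intervention.

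**The concern.** Two things look wrong. First, the plan names more than one test of the same hypothesis and does not rank them. Each secondary outcome can yield a crude chi-square p-value and one or more logistic p-values, and the covariates of the multivariable model depend partly on which baseline differences turn up. If the results disagree, nothing written in advance settles which one counts.

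Second, the test given to the arm comparison pools the strata. Blocking within strata balances severity between the arms. When severity also predicts the outcome, the pooled variance includes between-stratum variation that cannot contribute to the arm difference. The test then rejects too rarely under the null and loses power under the alternative. The planned chi-square of referral by presence or absence of AUD does not repair this, because it compares severity groups and not arms.

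**Working it through.** **The plan's own figure.** No power, rate or effect size is given for either secondary outcome. The power table covers the primary outcomes: 0.84, 0.82 and 0.78 at 72, 68 and 63 per arm. A two-sample noncentral t calculation with d = 0.5 (Cohen's medium, assumed) and two-sided alpha 0.05 gives 0.846, 0.825 and 0.795, all within 2 points. One-sided alpha gives 0.912, 0.898 and 0.877, which does not fit. Two-sided 0.05 is therefore used below.

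**Inputs.** AUD to risky drinking 2:1 and equal arms (Sample Size and Power Considerations): 48 + 24 = 72 per arm at 20% loss to follow-up. The stratum rates are assumptions and are shown over a range.

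**Size of the unstratified chi-square.** Let p be the overall event proportion, (2·p_AUD + p_risky)/3, and let

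r = within-stratum variance / total variance = {[2·p_AUD(1 − p_AUD) + p_risky(1 − p_risky)]/3} / {p(1 − p)}.

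With exact balance within strata, the large-sample true size of the nominal 0.05 test is 2·[1 − Φ(1.96/√r)].

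Example, 50% (AUD) and 10% (risky): p = 1.1/3 = 0.3667. Total variance = 0.3667 × 0.6333 = 0.2322. Within-stratum variance = (2 × 0.25 + 0.09)/3 = 0.1967. So r = 0.847, and the true size is 2·[1 − Φ(2.13)] = 0.033.

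**Power.** Simulation with 400,000 trials per scenario, 72 per arm and a common odds ratio of 2.5 (assumed). The Pearson chi-square without continuity correction is compared with a Cochran-Mantel-Haenszel (CMH) test stratified by severity.

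| Usual-care rate, AUD / risky | Gap (points) | True size, chi-square | Power, chi-square | Power, CMH | Loss (points) |
|---|---|---|---|---|---|
| 50% / 50% | 0 | 0.050 | 0.757 | 0.757 | 0.0 |
| 50% / 40% | 10 | 0.049 | 0.768 | 0.768 | 0.0 |
| 60% / 40% | 20 | 0.046 | 0.714 | 0.726 | 1.2 |
| 40% / 20% | 20 | 0.046 | 0.745 | 0.749 | 0.4 |
| 30% / 10% | 20 | 0.044 | 0.662 | 0.691 | 2.9 |
| 50% / 20% | 30 | 0.041 | 0.718 | 0.732 | 1.4 |
| 40% / 10% | 30 | 0.039 | 0.655 | 0.702 | 4.7 |
| 50% / 10% | 40 | 0.033 | 0.621 | 0.687 | 6.6 |
| 60% / 10% | 50 | 0.026 | 0.534 | 0.642 | 10.8 |
| 70% / 10% | 60 | 0.018 | 0.390 | 0.574 | 18.4 |

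With an odds ratio of 3.0 the losses are similar, for example 0.782 against 0.831 at 50% / 10%, or 5.0 points. The simulated size of the CMH test stayed between 0.044 and 0.055; the departures from 0.05 come from discreteness at these sample sizes.

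**If the effect differs by stratum.** With the whole effect in the AUD stratum (30% to 50%, risky drinkers 10% in both arms), power is 0.414 for the chi-square and 0.451 for CMH. The stratified test remains the better of the two.

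**The case against.** The strongest reply is that the plan already contains the remedy. It names logistic regression as the test, and the multivariable model includes both arm and AUD. A reader might infer from the chi-square sentences that severity is left out of the secondary analysis altogether; the documents do not support that. What stands against the reply is that the sentence naming logistic regression lists no covariates, while the model that includes AUD is presented as a further step and not as the test.

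A reader might also infer that both outcomes lose power. That goes too far. The expected severity effect is stated for referral only. Under Treatment as Usual, the brief-intervention reminder follows a positive AUD-C, which is an entry requirement in both strata. With equal stratum rates nothing is lost.

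The referral gap may also be modest. Risky drinkers can be referred because of their responses, previous treatment or a high AUDIT score. A documented discussion of referral counts as referral, and in usual care the decision rests with the clinician. This is a fair reason to show the whole range and not only wide gaps.

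Finally, these are secondary outcomes, the power section is confined to the primary hypotheses, and the error is in the safe direction. All of that stands, and it limits the importance of the point. It is no reason to leave the main test unnamed.

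**Conclusion.** The point holds in a limited form. For both outcomes, the plan does not say which analysis decides the hypothesis, and the chi-square assigned to the arm comparison omits the randomisation stratum. That follows from the text and needs no assumption.

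The power cost is supported for referral only, and its size depends on stratum rates that the documents do not give. At 72 per arm it is nil for gaps up to 10 points, about 0-3 points of power at a 20-point gap, about 1-5 at 30, and about 5-18 at 40 to 60. These figures assume a 2:1 severity split, balance within strata, two-sided alpha 0.05 and a common odds ratio of 2.5 to 3.0. For brief intervention a loss is possible but not shown.

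The reading that the chi-square is invalid or produces false positives is not supported: its large-sample size is at or below 0.05 in every scenario.

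**What to change.** For each secondary outcome, name one main test of treatment that includes the severity stratum: either CMH stratified by severity, or logistic regression with arm and the AUD indicator. Bring the overall-design paragraph and the two Secondary Hypothesis paragraphs into line with that choice. Label the crude chi-square descriptive and the wider multivariable model supportive, and correct the purpose clause in the referral paragraph.

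Report the common odds ratio with its 95% confidence interval. Because the Stratification section expects the effect to differ between strata, give the stratum-specific estimates beside it.

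The cost is SAP wording only. No extra participants or data are needed, and the stratified test gives up essentially no power even if severity turns out not to matter (0.757 for both tests at equal rates).

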Based on the results of the MINI Alcohol Scale, the research assistant will stratify each participant as having either risky drinking or an alcohol use disorder. Veterans stratified to the risky drinking group reflect a population of individuals among whom brief interventions have been most frequently demonstrated to be efficacious. In contrast, the efficacy of brief intervention among individuals with Alcohol Use Disorder has rarely been studied. Because we undertake this study as a pragmatic clinical trial, we do not want to exclude these individuals from participation; therefore we are stratifying our sample for two purposes. First, stratification will enable us to examine a priori the effectiveness of the Relational Agent on primary and secondary outcomes separately in these two strata. As described below, we hypothesize that the effect of the intervention will vary between the two strata. Second, stratification allows tailoring of the intervention to each stratum; we will configure the Relational Agent always to recommend referral for further evaluation and treatment to Veterans in the Alcohol Use Disorder group, whereas it will only recommend referral to Veterans meeting certain response criteria within the risky drinking group (no desire to change, wish to discuss drinking with a person instead). After the research assistant determines the stratum, the research assistant and Veteran proceed to randomization.

Randomization

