When session 1 is over, the research assistant will print out the patient feedback report for the participant, and make sure they are scheduled for session 2 and the 3 month research interview. The patient feedback report will contain information about the participant's drinking and their list of pros and cons (see Appendix B). The clinic report will contain information about the participant's drinking, and whether or not a referral was agreed upon. The information from the clinic report will go into a progress note in CPRS, and will be

used for referral if needed. The research assistant will check the clinic report to see if a referral is indicated, and contact [name] or [name] if a consult (referral) is indicated. [name] or [name] will speak with the participant on the phone to gather information for the consult and place the consult for the participant. If, in the unlikely event that either [name] or [name] are not available, the research assistant will contact the postdoctoral fellow working on this project, or walk the participant down to the offices of the Primary Care Mental Health staff for assistance. If there are any concerns about suicidality or homicidality from the telephone consult process, the research assistant will walk the participant over to Primary Care Mental Health staff for assistance. If they are not available the research assistant will alert the primary care team and hand off the patient to one of the PCC staff who can bring the patient to urgent care. See “Human Subjects – Protection Against Risk” for more detail.

When the participant returns for session 2, the research assistant will again set up the computer for the participant and allow them to use the program in privacy, using headphones. At the end of the session, the research assistant will print out the patient feedback report, confirm the 3 month follow-up appointment, and check the clinic report for instructions. If a referral is needed the research assistant will follow the same procedure as above. Veterans receive \$10 in for completing questionnaires after session 2.

The research assistant will also ask the Veteran to fill out the System Usability Scale and the ECA Questionnaire.

Three-Month Follow-up Interview

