We will use these instructions and, as done by Hawkins et al, we will provide reviewers with examples that satisfy each of the above components of brief alcohol counseling. Similarly, we will follow the approach of Hawkins et al in ascertaining referral for alcohol problems. Referral to alcohol treatment will be defined as a documented discussion in CPRS of referral for VA or non-VA services to address alcohol misuse or a scheduled appointment for VA services. We will train reviewers to identify and abstract information of any referral to VA or non-VA alcohol treatment services and document type of referred services (e.g., addiction specialty care, non-VA primary care services?) and date of referral appointment. Alcohol treatment services will be defined as any of the following with documentation indicating the purpose of the service was to evaluate or address alcohol misuse: VA inpatient or outpatient specialty-care addiction services, VA alcohol-related telephone counseling, or referral to non-VA facility for alcohol treatment. Reviewers will also be instructed to indicate if a discussion of a treatment referral was documented in CPRS without actual referral being made. For Veterans who received appointments to address alcohol misuse, reviewers will ascertain the date Veterans attended their referral appointment.

In addition, we will abstract and record other Mental Health diagnoses, especially Substance Use Disorders, PTSD, and TBI, to describe the sample and examine any subgroup differences.

[name], an experienced primary care physician and active user of CPRS, will train the research assistants to conduct the CPRS review and abstraction. The research assistants will be blinded to the treatment status of the Veterans. [name], who will also be blinded to the treatment status, will oversee the data abstraction and ensure its quality and accuracy. Abstracted data will be entered into the REDCAP database for eventual conversion to SPSS format for analysis.

Study Data Management

Telephone communications. We will have one telephone line where participants or clinic staff can call and leave messages. Research staff will answer this phone or return calls promptly.

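### The expectation that Veterans with alcohol use disorder are referred more often in either arm is tested by one chi-square pooled over arms, so a positive result may largely reflect how the agent is programmed

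*Combined protocol and SAP*

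**What the plan says.** The second of the two secondary hypotheses in Statistical Analysis concerns referral to specialty treatment. After the comparison of arms, the plan adds an expectation that "Veterans with alcohol use disorders will be more likely to be referred regardless of group" and proposes to test it on its own: "we will use chi-square to compare rates of referral based solely on presence or absence of alcohol use disorders". The logistic model that follows has indicators for arm and for AUD. It lists no product term, and no comparison of AUD with risky drinkers inside either arm is described.

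Other sections describe how referrals arise in the agent arm:

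- Stratification: "we will configure the Relational Agent always to recommend referral for further evaluation and treatment to Veterans in the Alcohol Use Disorder group". For risky drinkers the recommendation is conditional and depends on particular answers they give.
- Relational Agent Intervention-procedure: a positive MINI, earlier substance abuse treatment, or an AUDIT score above 20 "will trigger a referral to specialty treatment at the end of the intervention". The MINI also defines the two strata.
- Same section: the clinic report shows if the Veteran accepted a referral, and its content is passed on: "The information from the clinic report will go into a progress note in CPRS".
- Review of the Computerized Patient Record System (CPRS): "Referral to alcohol treatment will be defined as a documented discussion in CPRS of referral for VA or non-VA services to address alcohol misuse"; a scheduled VA appointment also qualifies.
- Dependent Variables: the main analysis accepts either CPRS or self-report as evidence of referral.

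**The concern.** The stated expectation is about both arms, but a table that collapses over arm can be significant because of one of them. In the RA arm, the variable being tested (AUD by MINI) is an input to the software that generates the recommendation. The recommendation reaches CPRS through the progress note, and a documented discussion is enough for the outcome, so even a declined recommendation may count.

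At stake is one descriptive conclusion. A significant pooled test would invite the statement that AUD status drives referral in either arm, when usual care might show no such difference.

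**Working it through.** **The plan's own figures.** The documents give no referral rate, sample size or power for this test. The power table (0.84, 0.82, 0.78) concerns the drinking outcomes. A two-sample t-test with d = 0.5 and two-sided alpha 0.05 gives 0.846, 0.825 and 0.795 for 72, 68 and 63 per arm, so the table is reproduced to within 2 points. It says nothing about the referral test.

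**Inputs from the documents.** 120 AUD and 60 risky drinkers, which with equal arms is 60/30 per arm. At 20% loss this is 48/24 per arm, or 96 AUD and 48 risky in total; at 30% loss it is 42/21 per arm. Alpha is 0.05, taken as two-sided.

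**Inputs assumed.** All referral rates. The TAU rate is set equal in the two strata, so there is no AUD effect in usual care.

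**Formula.** With equal arms, each pooled stratum rate is the mean of the TAU and RA rates. The Pearson statistic without continuity correction is (pA - pR)² / [p(1 - p)(1/nA + 1/nR)], where p is the overall rate. With 96 and 48, 1/96 + 1/48 = 0.03125.

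| RA rate, AUD / risky (TAU 30% / 30%) | Pooled AUD / risky | Overall p | Chi-square | p-value |
|---|---|---|---|---|
| 90% / 30% | 60% / 30% | 0.50 | 0.09 / (0.25 × 0.03125) = 11.5 | 0.0007 |
| 90% / 60% | 60% / 45% | 0.55 | 0.0225 / (0.2475 × 0.03125) = 2.9 | 0.09 |
| 70% / 40% | 50% / 35% | 0.45 | 0.0225 / (0.2475 × 0.03125) = 2.9 | 0.09 |

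**Range.** Simulation of the pooled test, 20,000 runs per setting, with the TAU rate equal in both strata at 10%, 20% or 30% and sizes from 60/30 to 42/21 per arm. The entries are the chance of declaring AUD Veterans referred more often.

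| RA rate, AUD | RA risky rate 10-30% | RA risky rate 50% |
|---|---|---|
| 100% | 98-100% | 79-96% |
| 90% | 91-100% | 58-77% |
| 70% | 58-100% | 16-24% |
| 50% | 19-91% | about 2% |

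If usual care ran the other way (AUD 10%, risky 20%) and the RA rates were 100% and 20%, the pooled test would still be positive in 99.7% of runs at 48/24 per arm.

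**Would adjusting for arm help?** No. A Mantel-Haenszel test stratified by arm still rejects in at least 99% of runs with an RA-arm AUD rate of 100% and a risky rate of 10-30%. Balancing or adjusting for arm leaves the RA-arm contrast in the average. Only a within-arm contrast or an interaction term separates the two.

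**The TAU arm alone.** Its two-sided false-positive rate is 4-6% when TAU has no AUD effect. Its power for an assumed 30% versus 10%, from the normal approximation for two proportions, is 57% at 60/30, 47% at 48/24 and 41% at 42/21. For 40% versus 10% it is 88%, 79% and 73%.

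**The case against.** The strongest reply is that the test is valid for what it literally describes. Randomization is stratified on AUD, so arm is balanced across strata and does not confound the contrast. A positive result with no difference in TAU is then a correct statement about the average over both arms. That stands as a description of the marginal comparison. It does not make the comparison a test of an expectation that is said to hold irrespective of arm.

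The Stratification section also promises to examine the agent's effect on secondary outcomes separately in the two strata. If all four cell rates were shown, a null difference in TAU would be visible. But that analysis compares arms within strata; it does not compare AUD with risky drinkers within usual care.

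A reader might go further and infer that the agent refers every AUD Veteran, so that significance is assured. The documents do not support this. The agent recommends or offers; agreement is recorded; consults go to willing participants; and CPRS reviewers are to mark discussions that led to no actual referral. Risky drinkers in the RA arm can also be referred, through earlier treatment, a high AUDIT score or certain responses. No rates are given, and under some plausible ones the pooled test is not significant.

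Nor does the point reach the trial's referral hypothesis. The comparison of TAU with TAU+RA has its own chi-square and logistic regression, and no sample size or primary outcome rests on the AUD contrast.

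**Conclusion.** The concern holds in a limited form. The pooled chi-square cannot establish that AUD Veterans are referred more often in either arm, because a positive result may come largely from the agent's configuration, and nothing else in the plan tests the association in usual care. This follows from the text alone.

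How probable a misleading positive is depends on assumed rates. It is very likely if nearly all AUD Veterans and few risky drinkers in the RA arm are counted as referred, which is the direction in which the documented-discussion definition pushes. It is far from certain if only agreed referrals count or if many risky drinkers also meet a trigger. Consequences are minor: one subsidiary analysis and its interpretation.

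**What to change.** In the referral paragraph of Statistical Analysis:

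1. Report AUD versus risky referral rates and their difference, with 95% confidence intervals, within each arm. Name the TAU arm as the informative contrast.
2. Add an arm-by-AUD term to the logistic model already planned. If nearly all AUD Veterans in the RA arm are counted as referred, the odds ratio may be unstable, and the within-arm rate differences should then carry the interpretation.
3. Keep the pooled chi-square, if wanted, only as a descriptive marginal comparison, and not as the test of the stated expectation.
4. State whether a recommendation that the Veteran declined counts as a referral in this analysis. The planned CPRS abstraction already allows the two to be separated.

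The cost is a change of wording before analysis, with no new data. The drawback is precision: the TAU contrast uses half the sample and has only about 41-57% power for 30% versus 10%, so a non-significant result there should be read from its interval and not as evidence of no association.
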